8.1.2.2. ADAS-Cog₁₃

The ADAS-Cog₁₃ is a rater-administered instrument that was designed to assess the severity of dysfunction in the cognitive and noncognitive behaviors characteristic of persons with AD (Rosen et al. 1984). The ADAS-Cog₁₃ should be administered by the same rater from visit to visit to reduce potential variability.

The cognitive subscale of the ADAS, the ADAS-Cog₁₃, consists of 13 items assessing areas of cognitive function that are the most typically impaired in AD: orientation, verbal memory, language, praxis, delayed free recall, digit cancellation, and maze-completion measures (Mohs et al. 1997). The ADAS-Cog₁₃ scale ranges from 0 to 85, with higher scores indicating greater disease severity.

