8.1.2.4. ADCS-ADL

The ADCS-ADL is a 23-item inventory developed as a rater-administered questionnaire that is to be answered by the participant's study partner (Galasko et al. 1997, 2004). The ADCS-ADL should be administered by the same rater from visit to visit to reduce potential variability.

The ADCS-ADL subset of items (items 6a and 7 to 23) for iADLs will be used as a secondary efficacy measure. The focus in the early symptomatic AD population is on the iADLs rather than the bADLs, which are thought to be affected in more severe stages of the disease. The range for the iADL score is 0 to 59, with lower scores indicating greater disease severity.

For each of the specific items, the study partner is first asked if the participant attempted the ADL during the past 4 weeks. If the participant did attempt the ADL, the study partner is asked to rate the participant's performance level based on a set of performance descriptions. Scores for each item and the overall score for the tool are calculated. The range for the total ADCS-ADL score is 0 to 78, with lower scores indicating greater level of impairment. Separate scores for the bADLs (0 to 19) will also be computed.

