4.2.2. Handling Missing Items in Calculating Total Scores

If any of the individual items for ADAS-Cog or ADCS-ADL are missing or unknown, every effort will be made to obtain the score for the missing item or items.

For ADAS-Cog₁₃, if 3 or fewer of a total of 13 items are missing, the total score (maximum = 85) will be imputed as follows: the total from the remaining items will be multiplied by a factor that includes the maximum score for the missing items. For example, if the first item, “Word-Recall Task,” which ranges from a score of 0 through 10 (maximum = 10), is missing, and the second item “Commands,” which ranges from a score of 0 to 5 (maximum = 5), is missing, then the multiplication factor = $85 / (85 - [10 + 5]) = 85 / 70 = 1.21$. Thus, the total score for this example will be the sum of the remaining 11 items multiplied by 1.21. The imputed number will be rounded up to the nearest integer. If more than 3 or fewer items are missing, the total score for ADAS-Cog₁₃ at that visit will be considered missing.

For the ADCS-iADL, if <30% of the items are missing, the total score will be imputed. The sum of the non-missing items will be prorated to the sum of total items. The imputed number will be rounded up to the nearest integer. If the nearest integer is greater than the maximum possible score, the imputed score will be equal to the maximum score. If >30% of the items are missing, the total score for ADCS-iADL at that visit will be considered missing. The same imputation technique will be applied to the ADCS-ADL total score. Note that, depending on the specific item responses that are missing, it is possible to have an imputed total score for both the ADCS-iADL and the ADCS-ADL, an imputed total score for one but not the other, or both total scores missing.

The iADRS score is calculated as follows: $iADRS \text{ score} = [-1(ADAS-Cog_{13}) + 85] + ADCS-iADL$ (Wessels et al. 2015). If either ADAS-Cog₁₃ or ADCS-iADL is missing, iADRS score will be considered missing.

For the CDR-SB score, if only 1 box (of 6) of the CDR is missing, the sum of the boxes will be imputed by prorating the sum from the other 5 boxes. If the score from more than 1 box is not available, the CDR-SB at that visit will be considered missing.

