4.8.2.2. Mixed Model with Repeated Measures (MMRM) Analysis

The change from baseline score on the iADRS at each scheduled post-baseline visit (according to the SoA) during the treatment period will be the dependent variable. The analysis model includes the fixed effects of treatment, visit as a categorical variable, baseline score, baseline-by-visit

interaction, treatment-by-visit interaction, and investigator site (pooled). Baseline covariates such as age and concomitant AChEI/memantine use at baseline (yes/no) will be included in the model. An unstructured covariance matrix will be used to model the within-subject variance-covariance of residual errors across visits. If the unstructured covariance structure matrix results in a lack of convergence, the following tests will be used in sequence:

- Heterogeneous Toeplitz covariance structure
- Heterogeneous autoregressive order 1 covariance structure
- Heterogeneous compound symmetry covariance structure, and
- Compound symmetry covariance structure

The Kenward-Roger approximation will be used to estimate the denominator degrees of freedom.

The treatment group contrast in LS mean progression and its associated p-value and 95% CI will be calculated for the treatment comparison of LY3372689 versus placebo using the MMRM model specified above.

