4.8.3.2. Delta Adjustment Tipping Point Analysis

Sensitivity to departures from the MAR assumption in the MMRM analyses will be investigated using a tipping point analysis (Carpenter & Kenward 2013). This method is a sensitivity analysis in multiple imputation (MI) under the missing-not-at-random (MNAR) assumption that searches

for a tipping point that reverses the study conclusion. Departures from MAR in the active treatment arms will be assessed assuming that participants who discontinue the study have, on average, efficacy outcomes after discontinuation that are worse by some amount δ compared to other similar participants with observed data (i.e., compared to a value which would have been assumed under an MAR model). A series of analyses will be performed with increasing values of δ until the analysis conclusion of a statistically significant treatment effect no longer holds. The value of δ that overturns the primary results will represent a tipping point. An interpretation of clinical plausibility of the assumption underlying the tipping point will be provided.

Mean changes from baseline in iADRS scores will be analyzed based on data observed while the participant remains on study as well as data imputed using MI methodology for time points at which no value is observed. Imputed values in the active treatment arms will first be sampled from an MAR-based MI model and then δ -adjusted as described below.

Missing-at-random-based imputations will be generated for iADRS scores at each time point, and then a value of $\delta = \{\Delta\}$ will be added to all imputed values in the active treatment arms prior to analyzing multiply imputed data. This approach assumes that the marginal mean of imputed participant measurements is worse by δ at each time point after discontinuation compared to the marginal mean of participants with observed data at the same time point. Analyses will be conducted with values of δ starting from 0 with increments of 0.10 until the null hypothesis can no longer be rejected.

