4.11.3. Analysis of Time to Clinical Progression

Any increase in CDR-GS from baseline at 2 consecutive visits during the double blinded study period is considered as meeting the criteria of time to substantial decline (MCID, Andrews et al. 2019; Wessels et al. 2022; Lansdall et al. 2023). A Cox proportional hazard model will be utilized to evaluate the hazards of progressing to the clinical worsening events as defined by CDR-GS by treatment arms in the Efficacy Evaluable analysis set in both moderate tau subpopulation and the full study population, respectively.

The analysis will be modeling time to first occurrence of the event as determined above. The ties will be handled using discrete method. The analysis will adjust for age at baseline, concomitant AChEI and/or memantine use at baseline (yes/no). The analysis will be conducted in both moderate tau subpopulation and full study population. The model will be stratified by investigator site (pooled). The model will also be stratified by baseline tau PET category when analyzing full study population. The hazard ratio (HR) for LY3372689-treated group versus placebo group, 95% CI and associated p- value will be provided.

To further evaluate the efficacy of LY3372689 in terms of delaying the substantial clinical worsening The time to substantial clinical progression as defined by iADRS and CDR-SB using the criteria of substantial decline (MCID, Andrews et al. 2019; Wessels et al. 2022; Lansdall et al. 2023) below may be conducted. A clinical worsening event is defined as meeting the criteria at 2 consecutive visits during the double blinded phase:

Endpoint \ baseline clinical status	mild cognitive impair (MCI)	mild AD
iADRS	5 points decrease from baseline	9 points decrease from baseline
CDR-SB	1 point or more increase from baseline	2 points increase from baseline

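### SAP 4.8.3.2 assumes active-arm dropouts do worse by δ but adds δ to iADRS, where higher is better, so a significant MMRM benefit would not tip

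*SAP*

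**What the plan says.** SAP 4.8.3.2 tests how far the missing-at-random assumption behind the iADRS MMRM can be relaxed. Missing values are first imputed under missing at random. A shift δ then "will be added to all imputed values in the active treatment arms prior to analyzing multiply imputed data". The values of δ run "starting from 0 with increments of 0.10 until the null hypothesis can no longer be rejected". The section states twice, once before this instruction and once directly after it, that the shift represents imputed active-arm outcomes being worse by δ.

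The direction of the scale is fixed elsewhere:

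- SAP 4.2.2, in the sentence that begins "The iADRS score is calculated as follows", defines iADRS as 85 minus ADAS-Cog13, plus ADCS-iADL.
- Protocol 8.1.2.2 says that ADAS-Cog13 "ranges from 0 to 85, with higher scores indicating greater disease severity".
- Protocol 8.1.2.4 says of the other component: "The range for the iADL score is 0 to 59, with lower scores indicating greater disease severity".
- SAP 4.11.3 counts a fall in iADRS as a worsening event, for mild cognitive impairment "5 points decrease from baseline".
- The MMRM in SAP 4.8.2.2 models "The change from baseline score on the iADRS at each scheduled post-baseline visit", with no sign reversal.

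**The concern.** The section's assumption and its instruction point in opposite directions. On a scale where higher is better, adding a non-negative δ makes active-arm dropouts look better than missing at random predicts. The δ placeholder has no sign of its own, but a grid that starts at 0 and rises makes it non-negative. Neither document reverses the scale or makes δ negative.

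SAP 4.2.1 handles dropout by likelihood methods that rely on missing at random or ignorable missingness, and I found no other missing-not-at-random analysis in either document. If the instruction is programmed literally, a borderline benefit could be reported as robust to any departure from missing at random. Two programmers could also read the same section and produce opposite results.

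**Working it through.** The section states no numerical result, and the power in the sample-size section is blacked out, so there is no plan figure to reproduce.

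**Step 1: direction.** iADRS = 85 − ADAS-Cog13 + ADCS-iADL. The best score is 85 − 0 + 59 = 144 and the worst is 85 − 85 + 0 = 0. One more point on ADAS-Cog13, or one fewer on ADCS-iADL, lowers iADRS by 1. Higher is better.

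**Step 2: effect of the shift.** If a fraction p of the active arm is imputed and shifted by s, the active-minus-placebo difference becomes d0 + p·s. With equal n per arm and common SD,

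z(s) = (d0 + p·s) / √[SD²/n + (SD² + p(1−p)s²)/n].

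As written, s = +δ. With the sign corrected, s = −δ.

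**Step 3: inputs.** From the documents: two-sided alpha 0.05 (SAP 4.1), hence a critical value of 1.96, and a δ grid of 0, 0.10, 0.20 and so on. Assumed, because the documents do not give them: n = 60, 80 or 110 per arm; SD of change 10, 13 or 16; starting z of 2.0, 2.2, 2.5 or 3.0; p = 0.25. The value of p is prompted by the expected completion of the 76-week treatment period, about 240 of 330. That is 72.7%, although the plan calls it 75%. p = 0.273 was therefore also run, at n = 80 and SD 13.

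**Step 4: as written (δ added).** Take n = 80, p = 0.25, SD 13 and starting z 2.0. The starting SE is 13 × √(2/80) = 2.056, so d0 = 2.0 × 2.056 = 4.11. At δ = 5, z = (4.11 + 1.25) / √[169/80 + (169 + 0.1875 × 25)/80] = 5.36 / 2.07 = 2.59.

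| δ added | 0 | 5 | 10 | 20 | 144 |
|---|---|---|---|---|---|
| z | 2.00 | 2.59 | 3.13 | 4.01 | 5.52 |

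In every scenario run at 25% or 27.3% imputed, the smallest z for δ from 0 to 144, the full width of the scale, was the starting value. Significance was never lost.

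**Step 5: sign corrected (δ subtracted).** With n = 80, p = 0.25 and SD 13:

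| Starting z | 2.0 | 2.2 | 2.5 | 3.0 |
|---|---|---|---|---|
| Worsening at which significance is lost (points) | 0.4 | 2.0 | 4.4 | 8.3 |

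Over all the assumed n and SD at 25% imputed, the tipping point runs from 0.3 points (for example n = 110, SD 10, starting z 2.0) to 11.6 points (n = 60, SD 16, starting z 3.0).

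**Step 6: multiple-imputation check.** A small simulation with 50 imputations and Rubin's rules started from a difference of 6.09 points and z = 2.42.

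| Shift (points) | 0 | 2 | 5 | 10 |
|---|---|---|---|---|
| z, δ added | 2.42 | 2.62 | 2.90 | 3.35 |
| z, δ subtracted | 2.42 | 2.22 | 1.91 | 1.40 |

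The direction agrees with the closed form.

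**The case against.** The best defence is that the intent is plain. The section gives the direction as worse twice and describes a search for the point that overturns the conclusion. On that reading δ is the size of a worsening and a single verb is wrong. A literal run would also give itself away, because z rises from the start, the loop finds no end, and there is no tipping point for the promised clinical interpretation. This stands as an account of what was meant. It does not rescue the instruction, which is the part a programmer would code.

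Four stronger readings are tempting, and the documents do not support them.

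- **That the trial's main conclusion is at risk.** The section speaks of overturning the primary results, but it sits under supplementary analyses and tests the MMRM, which is itself a sensitivity analysis. The success criterion is a posterior probability from the DPM (SAP 2). The gated tests in SAP 4.9.2.1 use the DPM for iADRS, the NCS2 spline model for the clinical secondaries and MMRM for tau PET. None depends on δ.
- **That the analysis can never tip at all.** This holds for a significant benefit. Tests are two-sided, so an active arm significantly worse than placebo would move towards the null as δ is added. A large δ also inflates the variance: z tends to √[np/(1−p)], about 5.2 at n = 80 and p = 0.25, and falls below 1.96 only with about 3 or fewer imputed participants. Even at 1% to 3% imputed (n = 80, SD 13), no crossing occurred up to δ = 144.
- **That one tipping value can be quoted, or that 25% is the imputed share.** The 25% is expected non-completion of treatment among all 330 participants. The analysis is confined to moderate tau (SAP 4.8), and participants who stop drug may stay in the study for efficacy assessment (Protocol 7.1). Only a range under stated assumptions is fair.
- **That sign rules are needed for the other scales.** The tipping-point analysis is planned for iADRS only.

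**Conclusion.** SAP 4.8.3.2 contradicts itself, and its operative instruction has the wrong sign for iADRS. The contradiction follows from the text alone and needs no assumption. The numerical contrast is illustrative: under the assumed inputs, the corrected analysis loses significance at a worsening of about 0.3 to 11.6 points, while the analysis as written does not lose it anywhere on the scale. The consequence is an uninformative missing-not-at-random check of a significant MMRM benefit. Estimates and decisions from the DPM do not change. The text is wrong as written rather than merely short of detail, and severity is moderate because the analysis is supplementary.

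**What to change.** In SAP 4.8.3.2, state that lower iADRS is worse and that δ is subtracted from imputed iADRS values in the active arms (equivalently, δ = 0, −0.10, −0.20 and so on, added) until significance is lost. Replace the unsigned placeholder for δ accordingly. Check the sign in the analysis program. If the analysis has already been run, confirm which sign was used, rerun it if δ was added, and record the correction in the clinical study report, where SAP 4.1 already places changes to analysis methods. The cost is one sentence in the SAP and one sign in the program. No new data are needed.

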4.9. Secondary Endpoint(s) Analyses

The analyses described in Section 4.9.1 and Section 4.9.2 will be conducted in moderate tau and full study populations separately with only analyses for moderate tau population being included in the graphical testing scheme described in Section 4.9.2.1.

4.9.1. Key Secondary Efficacy Endpoint Analysis

The key secondary objective of this study is to test the hypothesis that LY3372689 slows cognitive and functional decline in early symptomatic AD participants with elevated cortical tau burden as measured by iADRS compared with placebo through end time point (76 -124 weeks). The model setup will be the same as described in Section 4.8.1 and Section 4.8.2, with the inclusion of the tau burden (moderate versus high) as defined by flortaucipir PET in the model as a baseline covariate. The time-PMRM (Section 4.8.3.2) analysis may be conducted to assess the treatment effect from time-saving perspective.

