4.4. End of Study Definition

A participant is considered to have completed the study if he or she has completed all required phases of the study including the last visit or the last scheduled procedure shown in the SoA.

5. Study Population

Prospective approval of protocol deviations to recruitment and enrollment criteria, also known as protocol waivers or exemptions, is not permitted.

Early symptomatic AD participants, as defined in the inclusion criteria (Section 5.1), will be enrolled into Study MTAE. The inclusion criteria ensure that participants meet clinical criteria for having an AD clinical syndrome and have biomarker evidence consistent with the presence of AD pathology (Jack et al. 2018). With the use of tau PET imaging, with or without plasma P-Tau levels, as part of the eligibility criteria, enrolled participants will be highly likely to meet pathological criteria for AD, including the presence of both key pathologies, brain amyloid plaque and aggregated tau neurofibrillary tangles. (Fleisher et al. 2020; Palmqvist et al. 2020). This study population is hypothesized to represent those that will most benefit from the mechanism of action of LY3372689, which is believed to reduce further accumulation of pathological tau but not remove existing tau; further, a population at the earlier stages of tau pathology may benefit the most from LY3372689 treatment. It is also necessary to enroll a population that is likely to demonstrate clinical decline in the timeframe of Study MTAE. Elevated levels of tau pathology have been associated with increased risk for clinical progression (Pontecorvo et al. 2019). Therefore, the inclusion criteria for Study MTAE are selected to identify a study population with known tau pathology targeted by LY3372689, at levels consistent with risk of short-term clinical progression.

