6.3. Measures to Minimize Bias: Randomization and Blinding

This is a double-blind study (study periods 2a and 2b), with design to maintain blinding to treatment. To preserve the blinding of the study, a minimal number of Lilly personnel will see the randomization table and treatment assignments before the study is complete.

For between-group comparability, participant randomization will be stratified by the investigative site, tau burden (moderate versus high) as defined by flortaucipir PET, and by prior or current use of any approved disease-modifying therapy for AD. Enrollment of high tau burden participants will be capitated at a predetermined proportion of the total enrolled population. Hence, study eligibility based on flortaucipir PET scan results may change as the study progresses. Assignment to treatment groups will be determined using an interactive web response system (IWRS). The IWRS will be programmed using the dynamic allocation (minimization) method of Pocock and Simon (1975), to balance the treatment arms using three factors: investigative site, tau burden, and prior or current use of any approved disease-modifying therapy for AD. This is to achieve balanced participant assignment between treatment arms as much as possible within each stratum and at the study level. Randomization into 1 stratum may be discontinued at the discretion of the sponsor.

Blinded site personnel will dispense study intervention and confirm that they have located the correct packages by entering a confirmation number found on the label into the IWRS.

The independent external DMC is unblinded to randomization.

If an investigator, site personnel performing assessments, or participant is unblinded, the participant must be discontinued from the study. In cases where there are ethical reasons to have the participant remain in the study, the investigator must obtain specific approval from a Lilly-designated Medical Monitor for the participant to continue in the study.

In case of an emergency, the investigator has the sole responsibility for determining if unblinding of a participant's treatment assignment is warranted for medical management of the event. The participant's safety must always be the first consideration in making such a determination. If a participant's treatment assignment is unblinded, Lilly must be notified immediately. If the

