4.8.1. Main Analytical Approach

The primary objective of this study is to test the hypothesis that LY3372689 slows cognitive and functional decline in early symptomatic AD participants with moderate cortical tau burden as measured by iADRS compared with placebo through end time point (76-124 weeks). This will be assessed using a DPM, evaluating possible slowing of disease progression with treatment of LY3372689 relative to placebo.

The main purpose of the DPM is to estimate a quantity known as the disease progression ratio (DPR), which measures the proportion of disease progression in active treatment arms relative to placebo arm. The iADRS score at baseline and each scheduled postbaseline visit (according to SoA) during the treatment period will be the dependent variable. The DPM is as follows:

$$Y_{ij} = 1_{j>0} \cdot e^{\theta_{T_i}} \sum_{v=1}^j \alpha_v + X_i \beta + \gamma_i + \varepsilon_{ij}, i = 1, 2, \dots, k; j = 0, 1, 2, \dots, l$$

where Y_{ij} denotes the clinical outcome at visit j for participant i , clinical outcome scores at baseline (prior to treatment) is Y_{i0} . The term $1_{j>0}$ is the indicator function that is 0 for $j = 0$ (baseline visit) and 1 otherwise. For post-baseline visits, the multiplication term $e^{\theta_{T_i}}$ is the DPR associated with the treatment group of participant i , $T_i \in \{\text{Placebo}, \text{LY}_{\text{low}}, \text{LY}_{\text{high}}\}$. $\theta_{\text{Placebo}} = 0$, $e^{\theta_{\text{LY}_{\text{low}}}}$ and $e^{\theta_{\text{LY}_{\text{high}}}}$ represent the DPR of the low dose and the high dose in relative to placebo, respectively. α_v ($v \geq 1$) denotes the mean change of placebo response from visit $v - 1$ to visit v . The parameter γ_i represents a subject-specific random intercept for participant i which is assumed to center the baseline main effect $\gamma_i \sim N(\mu_{BL}, \sigma_{BL}^2)$, where the parameter μ_{BL} models the mean baseline score across arms. ε_{ij} is the error variance which is assumed to follow $\varepsilon_{ij} \sim$

$N(0, \sigma^2)$. X_i denotes subject specific baseline covariates that will be included in the model and β represent the associated fixed effects. Stratification variables used for randomization such as investigator site (pooled) will be included in the model. Baseline covariates such as age and concomitant AChEI/memantine use at baseline (yes/no) will also be included in the model.

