4.8.2.1. Natural Cubic Spline (NCS) Analysis

A NCS model with 2 degrees of freedom (NCS2) (Donohue et al. 2023) will be used to estimate the difference in the change in iADRS score between the treatment arms. The NCS2 model has 3 knots over the observation time will be placed: 2 at the boundaries (minimum and maximum observation time), and 1 internal knot at the median observation time. The baseline estimates are restricted to be the same for all treatment arms. The model will be estimated using restricted maximum likelihood method (RMLE).

The iADRS score at baseline and at each of the scheduled post-baseline visits (according to SoA) will be included in model as a dependent variable. The analysis model will include the fixed effects of NCS basis expansion terms (two terms), NCS basis expansion term-by-treatment interaction (two terms), age at baseline, AChEI/memantine use at baseline (yes/no), and investigator site (pooled). Visit will be treated as a continuous variable with values equal to weeks between baseline and post-baseline exam dates, and the NCS basis function will be derived using these visits in weeks. An unstructured variance-covariance structure matrix will be used to model within-subject variance-covariance of residual errors across visits where visits are modeled as a categorical variable. If the unstructured variance-covariance structure matrix results in a lack of convergence, the following structures will be used in sequence:

- Heterogeneous Toeplitz covariance structure
- Heterogeneous autoregressive order 1 covariance structure
- Heterogeneous compound symmetry covariance structure, and
- Compound symmetry covariance structure

Mean change from baseline values, and the comparisons between change from baseline values by treatment arms will be estimated through the proper contrast set up. The Kenward-Roger approximation will be used to estimate the denominator degrees of freedom.

Percent slowing comparing to placebo group will be calculated as the least-squares (LS) estimates of differences in change from baseline between treatment groups, then divided by the LS estimates of mean change from baseline value from placebo group. A 95% CI for this percent slowing is calculated based on a Delta method (Beyene et al. 2005).

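### In the full-population NCS2 and MMRM models, tau burden enters as a time-constant covariate only; adding tau-by-time terms is a cheap precision gain, probably small

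*SAP*

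**What the plan says.** Protocol 6.3 makes tau burden a randomisation factor: "participant randomization will be stratified by the investigative site, tau burden (moderate versus high) as defined by flortaucipir PET". Protocol 9.4.3 calls for the full-population iADRS analysis to adjust for tau burden and does not give the form. SAP 4.9.1 gives it: the models of SAP 4.8.1 and 4.8.2 are reused, "with the inclusion of the tau burden (moderate versus high) as defined by flortaucipir PET in the model as a baseline covariate".

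Covariates enter those models as follows.

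- **DPM (SAP 4.8.1).** The outcome includes the baseline score. X_i "denotes subject specific baseline covariates that will be included in the model and β represent the associated fixed effects". The term has no visit index and stands outside the progression term.
- **NCS2 (SAP 4.8.2.1).** The outcome again includes baseline. The spline is crossed with treatment only, and the covariates follow as main effects: "NCS basis expansion term-by-treatment interaction (two terms), age at baseline", then AChEI/memantine use and pooled site.
- **MMRM (SAP 4.8.2.2).** The outcome is "The change from baseline score on the iADRS at each scheduled post-baseline visit". Baseline score and treatment are each crossed with visit; the other covariates are main effects.

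SAP 4.9 keeps full-population analyses out of the graphical testing scheme. SAP 4.12.1 does plan subgroup-by-visit terms, but in the subgroup analyses only.

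**The concern.** The treatment effect is judged on decline from baseline. A stratum variable helps precision to the extent that it explains decline. A term that is the same at every visit, baseline included, explains where a participant starts and not how fast the participant falls. Protocol Section 5 links tau to decline: "Elevated levels of tau pathology have been associated with increased risk for clinical progression". If the two strata differ in rate, that difference stays in the residual of the full-population models although the factor was measured, used in allocation and nominally included. What is at stake is some precision in the supporting analyses of the only key secondary objective.

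**Working it through.** **No plan figure to reproduce.** No power is given for the key secondary analysis, and the inputs behind the general power statement in SAP Section 5 are redacted. The visible 2.4% false-positive rate cannot be rebuilt without them.

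**Step 1: what a constant term does.** Let H = 1 for high tau.

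- NCS2: E[Y(t)] = mu + b·H + f(t) + treatment·g(t), with t = 0 in the data. In Y(t) − Y(0) the term b·H cancels.
- MMRM: E[change at visit j] = b·H + other terms. The term stays but is equal at the first and last visit, so it fits only an average of a gap that grows with time.

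**Step 2: rough size.** If a fraction p of participants is high tau, the strata differ by g points in Week-76 decline, and SD is the within-stratum SD of change, ignoring tau inflates the variance by about 1 + p(1 − p)g²/SD².

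- p = 0.25, g = 5, SD = 13.9: 1 + 0.1875 × 25 / 193.2 = 1.024.
- p = 0.50, g = 10, SD = 11.4: 1 + 0.25 × 100 / 130.0 = 1.192.

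**Step 3: full calculation.** Generalised least squares with unstructured covariance and 80 completers per arm (SAP Section 5). Assumed, because the documents do not say: high-tau share 10–50%, gap 2, 5 or 10 iADRS points at Week 76, SD of change 11.4 or 13.9, baseline gap 4 points. V is the variance of the Week-76 contrast relative to the model with tau-by-time terms. Power is set at 80% for that model (two-sided 0.05), so power = Phi(2.802/√V − 1.96).

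| High share, gap, SD | MMRM: V without tau / with constant tau | Power, constant | NCS2: V without tau / with constant tau | Power, constant |
|---|---|---|---|---|
| 25%, 2, 13.9 | 1.006 / 1.003 | 79.9% | 1.006 / 1.004 | 79.8% |
| 25%, 5, 13.9 | 1.029 / 1.018 | 79.3% | 1.030 / 1.027 | 79.0% |
| 25%, 5, 11.4 | 1.044 / 1.022 | 79.1% | 1.047 / 1.041 | 78.4% |
| 50%, 5, 11.4 | 1.058 / 1.029 | 78.9% | 1.063 / 1.055 | 77.9% |
| 25%, 10, 11.4 | 1.160 / 1.089 | 76.6% | 1.178 / 1.165 | 73.8% |
| 50%, 10, 11.4 | 1.212 / 1.118 | 75.5% | 1.236 / 1.220 | 71.8% |

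Check of the last NCS2 entry: 2.802/√1.220 − 1.96 = 0.577, and Phi(0.577) = 0.718.

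In NCS2 the constant term recovers little of the inflation. For a 5-point gap the fitted shift is 4.4 to 4.7 points, of which 4 is the assumed baseline gap. In MMRM it takes up 1.3 to 1.6 of the 5 points.

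**Step 4: does the change move the estimate?** NCS2 and MMRM are linear. With strata balanced across arms, the treatment contrast is the head-count average of the stratum effects with or without tau-by-time terms. In trial fits with unequal effects in the two strata it did not move.

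The DPM is multiplicative and behaves differently. With shared placebo increments it weights strata roughly by share × decline. A tau-specific progression term weights them roughly by share × decline². Take 30% high tau declining twice as fast. The high-tau weight goes from 0.6/1.3 = 0.46 to 1.2/1.9 = 0.63. With a moderate-tau disease progression ratio (DPR) of 0.65:

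- high-tau DPR 0.85: the pooled DPR goes from about 0.74 to 0.78 (simulated means 0.72 and 0.77);
- high-tau DPR 1.0: from about 0.81 to 0.87 (simulated means 0.80 and 0.88).

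Those simulations used 110 per arm, placebo decline 10, slope SD 9, residual SD 5, 25% dropout and 300 replicates per cell. Power without and with the progression term was 63% and 72% for a common DPR, 44% and 37% for high-tau DPR 0.85, and 27% and 12% for 1.0. A second run with the same decline ratio and DPRs (250 replicates per cell) gave 77% and 81%, 50% and 43%, and 26% and 15%. Monte Carlo error is about 3 points per figure. The levels differ between runs; the direction agrees.

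**The case against.** The best defence is that little is lost. The gap between strata is not given anywhere. For gaps up to 5 points the loss is about 2 points of power or less. NCS2 and MMRM support the DPM here, nothing in the full population is alpha-controlled, and SAP 4.12.1 already estimates tau subgroups with time-varying terms. All of this stands and limits the weight of the point. The subgroup model, however, yields stratum effects and does not tighten the pooled contrast.

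A reader might infer more than the documents support.

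- *That rate of decline was the reason for stratifying.* Protocol 6.3 gives comparability between groups. Protocol Section 9 gives an expected smaller benefit in high tau as the reason for focusing on moderate tau. The Section 5 sentence justifies enrolling people with elevated tau and does not compare high with moderate.
- *That decline is unadjusted in every model.* In MMRM the constant term acts on change and takes up part of the gap.
- *That the estimate is biased.* With a common proportional effect and balanced strata, the mean log DPR was within 0.007 of the model with tau-by-time terms.
- *That the main DPM should get a tau-specific progression term.* It gains power only if both strata benefit equally. Under the Protocol's expectation of less benefit in high tau, it lost power and moved the pooled DPR.

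**Conclusion.** The point holds as one of efficiency, limited to NCS2 and MMRM in the full population. On a plain reading, SAP 4.9.1 adds tau burden without any time-varying term. The cost is a Week-76 contrast variance inflated by 0.2–22% in NCS2 and 0.1–12% in MMRM over the assumed ranges. The 8-point loss of power needs a 10-point gap, 50% high tau and the smaller SD in NCS2; the corresponding MMRM loss is 4.5 points. All sizes rest on stratum decline rates, a high-tau share and SDs that the documents do not state, and on an 80% anchor chosen for comparison. If the strata decline equally, nothing is lost by the plan as written. The primary moderate-tau analysis and the testing graph are untouched.

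**What to change.** In SAP 4.9.1, for the full-population analyses only:

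- NCS2: keep the tau main effect and add tau burden × the two NCS basis terms.
- MMRM: keep the tau main effect and add tau burden × visit.
- DPM: leave the main model unchanged. If a tau-specific progression term is of interest, report it as a labelled sensitivity analysis, with a note that it gives the faster-declining stratum more weight.

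The cost is SAP wording and a few degrees of freedom: two parameters in NCS2, and in MMRM six beyond the main effect for the seven scheduled iADRS visits from Week 12 to Week 88. If double-blind data have already been unblinded, report the extended NCS2 and MMRM as labelled sensitivity analyses beside the pre-specified ones.
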